#### Secondary outcomes

- ! Early definitive treatment rate in 2019 vs. 2020: defined as treatment in accordance with the current guidelines (cholecystectomy or ERCP with endoscopic sphincterotomy during the same hospital admission or within 2 weeks of discharge)
- ! 30-day hospital readmission rate in 2019 vs. 2020: defined as hospital readmission within 30days from discharge for recurrent biliary AP while awaiting interval cholecystectomy, or due to post-cholecystectomy complications
- ! Predictive factors of morbidity and mortality in patients with biliary AP

The compliance of surgeons to the most up-to-date international guidelines on biliary AP will be assessed through the analysis of the following attitudes:

! Use of scoring systems for the diagnosis and severity grading of biliary AP

- ! Use of lipase dosage (for the diagnosis) and CRP (for the severity grading) during the diagnostic workup
- ! Use of Ultrasound scan, CT scan, MRCP, and endoscopic Ultrasound scan (EUS) in the correct way and timing
- ! Use of early ERCP and sphincterotomy in case of cholangitis and/or choledocholithiasis
- ! Use of percutaneous and/or endoscopic drainage in case of infected pseudocyst or necrosis
- ! Timing of surgical necrosectomy
- ! Timing of re-laparotomy in case of open abdomen strategies
- ! Use of prophylactic antibiotics/antifungals
- ! Use of somatostatin analogs
- ! Use of early enteral feeding
- ! Use of early definitive treatment strategies, including cholecystectomy and/or ERCP and sphincterotomy

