#### Statistical analysis

The dichotomous variables will be expressed as numbers and percentages, while continuous variables will be expressed as mean and SD, or median and IQR (minimum and maximum values). Student's t test or ANOVA will be used for comparisons of continuous variables between groups. Chi-squared test or Fisher's exact test, as appropriate, will be used for analysis of categorical data. Multilogistic

regression models will be used to investigate clinical attitudes, physical, laboratory, and radiologic variables predictive of morbidity and mortality. A value of P < 0.05 will be considered statistically significant.

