## Section 10 – 30-day Morbidity

- ! Gastric outlet obstruction (Yes/No)
- ! Pseudocyst (Yes/No)
- ! Infected necrosis (Yes/No)
- ! Endoscopic drainage of pseudocyst/walled-off necrosis (Yes/No)
- ! CT-guided fine needle aspiration in case of infected pseudocyst/walled-off necrosis (Yes/No)
- ! Surgical necrosectomy (Yes-laparoscopic/Yes-open/No)
- ! Timing of surgical necrosectomy (< 2 weeks from the onset of symptoms/2-4 weeks)>4 weeks)
- ! Setting of surgical necrosectomy (Upfront/After failure of endoscopic necrosectomy/After failure of endoscopic and percutaneous necrosectomy)
- ! Cystogastrostomy (Yes-endoscopic/Yes-surgical/No)
- ! Abdominal compartment syndrome (Yes/No)
- ! Open abdomen (Yes/No)
- ! Timing of re-exploration (24-48 hours/48-72 hours/>72 hours)
- ! Bleeding (Yes/No)
- ! Bowel ischemia (Yes/No)

- ! Bowel fistula (Yes/No)
- ! Necrotizing cholecystitis (Yes/No)

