## Section 11 – Medical Therapy

- ! Antibiotic prophylaxis (Yes/No)
- ! Antifungal prophylaxis (Yes/No)
- ! Use of somatostatin analogs (Yes/No)
- ! Nutritional support on admission (Oral/Enteral via nasogastric feeding tube/Enteral via nasojejunal feeding tube/Total parental nutrition/Nihil per os)

Section 12 – Cholecystectomy (Yes-within 3 days/Yes-within 7 days/Yes-within 14 days/No-delayed cholecystectomy)

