## Section 13 – 30-day Overall mortality (Yes/No)

## Section 14 – Post-cholecystectomy 30-day morbidity and mortality

- ! Post-cholecystectomy morbidity (Yes/No)
- ! Post-cholecystectomy mortality (Yes/No)
- ! 30-day hospital readmission (No/Yes-due to surgical complications/Yes-due to recurrent pancreatitis while awaiting interval cholecystectomy)

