16. Enteral nutrition	! Enteral nutrition is recommended to prevent gut failure and infectious complications. Total parenteral nutrition (TPN) should be avoided but partial parenteral nutrition integration should be considered to reach caloric and protein requirements if enteral route is not completely tolerated. Both gastric and jejunal feeding can be delivered safely (1A).
17. Indications for emergent ERCP	
 
! Routine ERCP with acute gallstone pancreatitis is not indicated (grade 1A).
 
! ERCP in patients with acute gallstone pancreatitis and cholangitis is indicated (grade 1B).
 
! ERCP in acute gallstone pancreatitis with common bile duct obstruction is indicated (grade 2B).
 
! ERCP in patients with predicted severe acute gallstone pancreatitis without cholangitis or common bile duct obstruction cannot be
 

	recommended at this time (grade 2B).
18. Indications for percutaneous/endoscopi c drainage of pancreatic collections	
 
Clinical deterioration with signs or strong suspicion of infected necrotizing pancreatitis is an indication to perform intervention (percutaneous/endoscopic drainage)
 

	After 4 weeks after the onset of the disease:
	– On-going organ failure without sign of infected necrosis
	– On-going gastric outlet, biliary, or intestinal
	obstruction due to a large walled off necrotic
	collection – Disconnected duct syndrome
	- Symptomatic or growing pseudocyst
	After 8 weeks after the onset of the disease:
	- On-going pain and/or discomfort (grade 1C)
19. Indications for surgical intervention	! As a continuum in a step-up approach after percutaneous/endoscopic procedure with the same indications
	
 
Abdominal compartment syndrome
 
Acute on-going bleeding when endovascular approach is unsuccessful
 
Bowel ischaemia or acute necrotizing cholecystitis during acute pancreatitis
 
Bowel fistula extending into a peripancreatic collection (Grade 1C)
 

20. Timing of surgery	Postponing surgical interventions for more than 4 weeks after the onset of the disease results in less mortality (2B).

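### Necrosectomy timing and early cholecystectomy can be recorded only in patients who live to surgery, so their association with 30-day death, if modelled as the plan implies, is biased even with no true effect

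*Combined protocol and SAP*

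**What the plan says.** The Primary objective is to find which guideline items, if disregarded, go with negative outcomes. Under Secondary outcomes the protocol states: "The compliance of surgeons to the most up-to-date international guidelines on biliary AP will be assessed through the analysis of the following attitudes". The list that follows includes "Timing of surgical necrosectomy" and "Use of early definitive treatment strategies, including cholecystectomy and/or ERCP and sphincterotomy".

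The Statistical analysis section says that "regression models will be used to investigate clinical attitudes, physical, laboratory, and radiologic variables predictive of morbidity and mortality". It names no covariates and no method that takes account of when an exposure or a death occurred.

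The CRF records the relevant data as follows:

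- Section 10, necrosectomy: "Timing of surgical necrosectomy (< 2 weeks from the onset of symptoms/2-4 weeks)>4 weeks", counted from symptom onset.
- Section 12, cholecystectomy: "Yes-within 3 days/Yes-within 7 days/Yes-within 14 days/No-delayed cholecystectomy", with no time origin and no code for death before surgery.
- Section 13, outcome: "30-day Overall mortality (Yes/No", with no day of death. Primary outcomes counts 30 days from admission for morbidity but gives no origin for mortality.
- Section 2: year of admission only.

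On necrosectomy timing, Table 1 item 20 reads "Postponing surgical interventions for more than 4 weeks after the onset of the disease results in less mortality (2B"; Table 5, advice 6, also favours a delay of four weeks.

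**The concern.** Both exposures are defined by an event that happens after admission, while deaths are counted over the same period. A patient planned for cholecystectomy on day 6 who dies on day 3 joins the unoperated group. A patient intended for necrosectomy in week 5 who dies in week 3 never enters the late category. Early cholecystectomy and late necrosectomy then look better than they are, and departing from the guideline looks harmful, even if timing does nothing. Adjusting for admission severity does not remove this, because the bias arises when timing is unrelated to risk.

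The primary objective is to produce such a list of items, and the rationale for the study is to build care bundles on it. For these two items the association with 30-day death would partly reflect who lived long enough to be classified.

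**Working it through.** **The plan's own figure.** The plan gives no calculation on this point. Its only design figure is 200 per group. That cannot be reproduced, because no alternative mortality is stated. It is used here only as n = 400, and the bias itself does not depend on it.

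**Cholecystectomy, no true effect.** Let p be the share planned for surgery within the window, independent of outcome. Let s be the probability, among planned patients who die within 30 days, that the operation comes before death. Planned survivors are all operated, so exposure odds are p/(1-p) in survivors and ps/(1-ps) in deaths:

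OR = [ps/(1-ps)] / [p/(1-p)]

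Overall mortality cancels. The OR is below 1 whenever any planned patient dies first.

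Assumed, not in the documents: p from 30% to 70%; surgery day uniform on 1-5 or 1-14 from admission; deaths spread evenly over 30 days, or early (exponential, scale 10 days, cut at day 30). With even deaths s = 1 - (mean surgery day)/30, so 1 - 3/30 = 0.90 and 1 - 7.5/30 = 0.75. With early deaths s = 0.732 and 0.480.

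Example, p = 0.3 and s = 0.90: (0.27/0.73)/(0.30/0.70) = 0.370/0.429 = 0.86.

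| Deaths | Surgery days | s | OR at p = 0.3 | OR at p = 0.7 |
|---|---|---|---|---|
| Even | 1-5 | 0.90 | 0.86 | 0.73 |
| Even | 1-14 | 0.75 | 0.68 | 0.47 |
| Early | 1-5 | 0.732 | 0.66 | 0.45 |
| Early | 1-14 | 0.480 | 0.39 | 0.22 |

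Simulation agrees to within 0.01 (0.45-0.87 for days 1-5, 0.21-0.68 for days 1-14).

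**How often early surgery is wrongly called protective** (nominal 2.5%, simulated studies). Non-severe patients number 80% x 400 = 320. From the Sample size section (10% overall; 20% severe at 30%) their mortality is (10% - 20% x 30%)/80% = 5%. Lower values are added as assumptions.

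| Setting | Even deaths | Early deaths |
|---|---|---|
| 400 patients, 10% | 3-60% | 12-99% |
| 400 patients, 5% | 1-38% | 3-90% |
| 320 non-severe, 5% | 1-31% | 1-83% |
| 320 non-severe, 3% | 0-21% | 0-61% |
| 320 non-severe, 1% | 0-5% | 0-14% |

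**Necrosectomy, no true effect.** More than 28 days from onset, with a lag of L days to admission, is more than 28 - L days from admission. With L of 0-5 the patient has survived at least 23 of 30 days; with L = 21, only 7. The documents give no lag. Inputs: mortality 15% and 30% (both in the Background, the latter for infected necrosis); intended day uniform on 3-56, 3-42 or 10-56 from onset (assumed). Counting operations within 30 days of admission, the null OR for more than 4 weeks against earlier is:

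- lag 0-5 days: 0.05-0.18;
- lag 5-14 days: 0.12-0.30;
- lag 10-21 days: 0.18-0.46.

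The upper ends, about 0.3 and 0.45 for the two longer lags, come from evenly spread deaths.

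**Necrosectomy at study size.** The Background figures give at most 20% x 38% x 400 = about 30 interventions, surgical or endoscopic. With 10-30 operations and a lag of 0-5 days, about 1-5 fall beyond 4 weeks, and 88-99% of studies have no death in that cell. Fisher's test is falsely significant in at most 0.1% (up to 15% if operations after day 30 are also counted).

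**The case against.** **The covariates are not named.** This stands as a limit. The link rests on the word attitudes, used in both sections, and on the primary objective. A reader might infer that the plan expressly puts these two items in a 30-day mortality model; it does not say so.

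**Necrosectomy is too rare to mislead.** Largely right at 400 patients. A reader might expect frequent false claims from so extreme an odds ratio, but the figures show an almost empty cell. The size also depends on the assumed lag. However, 400 is a minimum, and a larger cohort would fill the cell without removing the bias.

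**The direction for cholecystectomy is known.** Mostly right. One might argue that the reader cannot tell the direction, but No-delayed is the only listed code that fits a patient who dies unoperated, so apparent protection is the expected result. The reverse (OR 1.4-3.6) needs sites to leave the item blank and those patients to be dropped. Nothing in the documents says this will happen.

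**The largest error rates come from a poor setting.** Also right. The 3-99% range uses the whole cohort at 10% mortality, with surgery planned regardless of severity. The objective calls for analysis by clinical presentation, and Table 1 item 22 defers surgery when there are fluid collections. Even 5% in non-severe disease is a high input: with the Background's roughly 5% overall case fatality (all acute pancreatitis), the same formula gives (5 - 6)/80, which is negative.

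**The simulated exposure is narrower than the protocol's.** The attitude also counts ERCP with sphincterotomy, and the protocol's early-treatment definition extends to two weeks after discharge. Neither was simulated, so the figures apply to the cholecystectomy item as coded on the CRF.

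**Conclusion.** The point holds in a bounded form and should be fixed. If the two items enter models of 30-day death, as the plan implies, their odds ratios are biased with no true effect, and nothing in the plan handles death before surgery.

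For cholecystectomy early surgery is expected to look protective: null OR about 0.45-0.87 (surgery on days 1-5) or 0.21-0.68 (days 1-14). The chance of a false protective finding runs from 0-14% in non-severe patients at 1% mortality to an upper bound of 3-99% in the whole cohort at 10%. For necrosectomy the null OR is about 0.05-0.18 with a 0-5 day lag and up to about 0.3-0.45 with longer lags; at 400 patients the result is an uninterpretable cell.

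The existence of the bias follows from the coding. Its size rests on assumed death timing, surgery timing, share operated and lag. A reader might extend the point to morbidity, to items fixed at admission, or to the 2019 against 2020 comparison; this argument does not reach them. Confidence is medium, chiefly because the covariates are not named.

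**What to change.** 1. Take the necrosectomy timing categories out of models of 30-day death and report them descriptively. This needs no new data.
2. State how patients who die without cholecystectomy are coded, and the day from which each window runs.
3. Where sites can supply day of cholecystectomy and day of death (or alive at day 30), as integers counted from admission, analyse cholecystectomy as a time-dependent exposure. Do so within the presentations for which the cited guidelines recommend it. The tables differ in scope, so the plan must name these presentations. State that the contrast is surgery against not yet surgery, that confounding by indication remains, and that few deaths limit adjustment.
4. Use a day-14 landmark only as a sensitivity analysis. It keeps 53% of deaths (even) or 21% (early): 21 or 8 of 40, and 9 or 3 of 16.
5. Where days cannot be obtained, report cholecystectomy timing descriptively and say that its association with 30-day death is not interpretable.

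In simulation the time-dependent analysis was falsely protective in 0-3.3% and falsely harmful in 0.6-5.3%, against 2.5% per side. This removes most of the distortion but is not exact with few deaths.

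Cost: two integers per patient, which identify no one, and one different model. Sites that have already entered data (the window is 01/03/2021 to 31/08/2021) must return to charts, and day of death may be missing at some. In non-severe disease 1-5% of 320 is only 3-16 deaths. Steps 1, 2 and 5 need no new data.

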#### Primary objective

! To evaluate which items of the current AP guidelines, if disregarded, correlate with

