23. Open abdomen	
 
! In patients with severe acute pancreatitis unresponsive to conservative management of IAH/ ACS, surgical decompression and use of open abdomen are effective in treating the abdominal compartment syndrome (2C).
 
! We suggest that clinicians should be cautious not to over-resuscitate patients with early SAP and measure intra-abdominal pressure regularly (1C).
 
! We suggest that the open abdomen (OA) be avoided if other strategies can be used to mitigate or treat severe intra-abdominal hypertension in SAP (1C).
 
! We recommend not to utilize the OA after necrosectomy for SAP (unless severe IAH mandates OA as a mandatory procedure) (1C).
 
! We recommend not to debride or undertake early necrosectomy if forced to undertake an early OA due abdominal compartment syndrome or visceral ischemia (1A).
 

24. Open abdomen management and temporary abdominal closure	
 
We recommend the use of negative pressure peritoneal therapy for OA management (1B).
 
We suggest fascial traction be added to NPWT methods (2B).
 
We suggest that further controlled studies be conducted on intra- peritoneal osmotic therapies in SAP (no recommendation)
 

25. Timing of dressing changes	! Open abdomen re-exploration should be conducted no later than 24– 48 h after the index and any subsequent operation, with the duration from the previous operation shortening with increasing degrees of patient non-improvement and hemodynamic instability (1C).
26. Timing for abdominal closure	! Early fascial and/or abdominal definitive closure should be the strategy for management of the open abdomen once any requirements for on-going resuscitation have ceased, the source control has been definitively reached, no concern regarding intestinal viability persist, no further surgical re-exploration is needed, and there are no concerns for abdominal compartment syndrome (1B).

From: Leppäniemi A, Tolonen M, Tarasconi A, Segovia-Lohse H, Gamberini E, Kirkpatrick AW, Ball CG, Parry N, Sartelli M, Wolbrink D, van Goor H, Baiocchi G, Ansaloni L, Biffl W, Coccolini F, Di Saverio S, Kluger Y, Moore E, Catena F. 2019 WSES guidelines for the management of severe acute pancreatitis. World J Emerg Surg. 2019 Jun 13;14:27. doi: 10.1186/s13017-019-0247-0. PMID: 31210778; PMCID: PMC6567462.

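### The re-exploration timing field has no code for under 24 hours or for patients never re-explored, so it does not match the recommendation it is meant to measure

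*Combined protocol and SAP*

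**What the plan says.** All references are to the combined protocol and SAP.

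- **CRF, Section 10 (30-day Morbidity).** After a yes/no item for open abdomen, the form asks for "Timing of re-exploration (24-48 hours/48-72 hours/>72 hours". These three classes are the whole response set.
- **Table 1, item 25 (Timing of dressing changes).** The recommendation reads "Open abdomen re-exploration should be conducted no later than" 24-48 h after the index and any later operation, "with the duration from the previous operation shortening with increasing degrees of patient non-improvement and hemodynamic instability". It gives no lower limit.
- **Secondary outcomes.** "Timing of re-laparotomy in case of open abdomen strategies" is one of the listed attitudes by which compliance will be assessed.
- **Primary objective.** The aim is "To evaluate which items of the current AP guidelines, if disregarded, correlate with" poor clinical outcomes, so each compliance item is also a candidate exposure.
- **Statistical analysis.** Multilogistic "regression models will be used to investigate clinical attitudes, physical, laboratory, and radiologic variables predictive of morbidity and mortality". The section gives no compliance coding rule, no adjustment set and no missing-data rule for this item.

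I found no instruction on how a site should enter a re-exploration performed before 24 hours.

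**The concern.** The field starts where the cited recommendation has no boundary. A patient taken back to theatre before 24 hours is within the limit and, by the recommendation's own wording, is likely to be among the less stable. The form cannot record that patient as what they were. The site must leave the field blank or choose a class that is not true, and different sites may choose differently.

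Patients with an open abdomen who were closed, or who died, before any re-exploration have no code either. A blank for them looks the same as missing data.

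Two results depend on the field: the compliance rate for the item, and the association between timing and outcome that the primary objective seeks.

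**Working it through.** The documents give no figure for re-exploration timing, so there is no plan figure to reproduce. The check sets the recommendation against the form and then does simple arithmetic on labelled assumptions.

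**1. Recommendation against form** (reading the upper limit as 48 h)

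| Interval | Table 1, item 25 | CRF code |
|---|---|---|
| under 24 h | within the limit; expected as instability rises | none |
| 24-48 h | within the limit | 24-48 h |
| 48-72 h | beyond it | 48-72 h |
| over 72 h | beyond it | >72 h |
| never re-explored (closed or died first) | not classified | none |

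Other timing fields do have an early class. CT, MRCP and endoscopic ultrasound have one below 24 hours (Section 7), ERCP has one within 24 hours and a No (Section 9), and the necrosectomy item in the same section reads "Timing of surgical necrosectomy (< 2 weeks from the onset of symptoms/2-4 weeks)>4 weeks".

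**2. Compliance rate.** Let a, b and c be the numbers re-explored before 24 h, at 24-48 h and later.

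- True rate = (a+b)/(a+b+c).
- Rate if early cases are blank = b/(b+c).
- Shortfall = ac/[(a+b+c)(b+c)], which is positive whenever a and c are both above zero.
- Rate if early cases are entered as 24-48 h = (a+b)/(a+b+c), which is correct.

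With an assumed a = b = c = 10, the true rate is 20/30 = 67% and the rate with blanks is 10/20 = 50%. The shortfall is 100/(30 × 20) = 17 points.

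**3. Outcome association.** If early cases are merged into 24-48 h, mortality in that class = (1-f) × p(24-48 h) + f × p(<24 h), where f is the early share of the merged class. The only figure from the documents is about 30% mortality in severe disease (Sample size). I use it as an anchor for the 24-48 h class; it is not an open-abdomen rate. The early share (10-40%), the early mortality (30-70%) and the late mortality (30% or 40%) are assumed.

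| Late mortality | f | Early mortality | Merged class | Difference from late, merged | Difference from late, early cases blank |
|---|---|---|---|---|---|
| 30% | any | 30% | 30% | 0 | 0 |
| 30% | 10% | 50% | 0.9×30 + 0.1×50 = 32% | +2 points | 0 |
| 30% | 40% | 70% | 0.6×30 + 0.4×70 = 46% | +16 points | 0 |
| 40% | 10% | 50% | 32% | -8 points | -10 points |
| 40% | 40% | 70% | 46% | +6 points | -10 points |

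The two ways of coding move the result differently. Its sign depends on rates the documents do not give.

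If a '<24 h' class is added but compliance is still analysed as up to 48 h against later, the crude difference equals the merged column. The new code does not remove that difference. It makes the early class visible so that it can be reported separately.

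**4. What severity adjustment can do.** Section 4 collects clinical scores, including APACHE II and the Revised Atlanta class, and organ failure at any time during the stay. Section 5 collects admission vital signs and ICU admission during the stay. None is dated to the re-exploration. Adjustment can reduce confounding by severity but cannot be relied on to remove it.

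**5. Never re-explored.** A patient coded >72 h must have survived that long without re-exploration. Those who died first have no code, so this selection cannot be examined.

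**The case against.** The strongest reply is that merging early cases into 24-48 h misclassifies nothing. Both lie within the cited limit, the compliance rate stays correct, and the contrast the primary objective needs (beyond the limit against within it) is the same with or without a separate early class. On this view what remains is confounding by indication, which calls for severity adjustment and not for a new code. That stands for the merged route. It does not cover the blank route, where the rate is wrong, and the form does not tell sites which route to take.

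A second reply is that blanks are this form's normal pattern for dependent fields. The yes/no item for open abdomen identifies who is eligible, and the necrosectomy timing item also lacks a not-applicable code. This largely stands. The ambiguity is confined to open-abdomen patients with an empty timing field, who may be early, never re-explored or missing.

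A third reply is that the item is one of eleven listed attitudes and concerns only open-abdomen patients. That also stands, and it limits the importance of the point.

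A reader might infer something stronger: that the form makes following the recommendation look lethal. The documents do not support that. Take 10 patients in each class with assumed mortality of 60%, 30% and 30%. Merging gives (6+3)/20 = 45% against 30%, an odds ratio of (9/11)/(3/7) = 1.9, with an approximate 95% interval of 0.4 to 9.6 at those numbers. Leaving the early cases blank gives 30% against 30%, an odds ratio of 1.0, and makes the compliant group look safer than its full 45%. If early cases die no more often than the others, neither route changes anything.

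**Conclusion.** The mismatch is certain from the text: the field has no class below 24 hours and no code for patients never re-explored, while the recommendation sets only an upper limit and shortens the interval with instability.

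The compliance rate is understated if sites leave early cases blank (67% to 50% on the assumed equal split) and correct if they enter them as 24-48 h. In the second case, early re-explorations driven by severity cannot be told apart in the outcome analysis.

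The size and direction of any bias in the timing-outcome association are unknown. Over the assumed ranges in the table, the crude difference runs from -10 to +16 points, according to coding and rates. The documents give neither the number of open-abdomen patients nor the share re-explored early; the number affected is probably small. These conclusions assume that the limit is read as 48 h. The point is worth fixing because the repair is cheap, but it does not touch the primary outcome counts or the 2019 versus 2020 comparison of mortality and morbidity.

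**What to change.** - **Form.** Add two responses to the re-exploration field: under 24 hours, and not re-explored (closed, or died before).
- **Compliance rate.** State that under 24 hours counts together with 24-48 h as within the cited limit.
- **Outcome analysis.** Report under 24 hours as its own class beside 24-48 h and over 48 h. Adjust for the severity data already collected in CRF Sections 4 and 5, and state that the result is open to confounding by indication.

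This concerns recording and analysis only and proposes no clinical interval.

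The cost is two response codes, one line of analysis text and a sparse extra class whose estimate will be imprecise. The data come from retrospective chart abstraction, so no new source is needed. If entry has already begun, open-abdomen records already entered would have to be checked again against the chart.

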#### **Primary outcomes**

- ! 30-day mortality: assessed by the number of AP patients with biliary etiology deceased during the non-pandemic period (2019) and the Covid-19 pandemic period (2020)
- ! 30-day morbidity: assessed by the number of AP patients with biliary etiology who experienced any type of AP-related complication within 30-days from the hospital admission during the non-pandemic period (2019) and the Covid-19 pandemic period (2020)

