#### **Study population**

All consecutive adult patients admitted to the participating surgical departments with a clinical and radiological diagnosis of biliary AP (with and without concomitant cholecystitis) between 01/01/2019 and 31/12/2020. Patient data will be retrospectively analyzed and demographic characteristics, comorbidity status, clinical and radiological findings, treatment strategies, 30-day morbidity and mortality will be evaluated.

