#### **Exclusion criteria**

Patients with AP of etiology other than gallstones; Pregnant patients.

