## Section 9 – Concomitant findings on admission

- ! Choledocholithiasis (Yes/Yes with common bile duct obstruction/No)
- ! Cholangitis (Yes/No)
- ERCP with sphincterotomy (Yes-within 24 hours/Yes within 24-48 hours/Yes within 48-72 hours/No)

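### Necrotizing cholecystitis already present on admission can be counted as 30-day morbidity and cannot be told apart from a later complication, which biases the early-cholecystectomy comparison by an unknown net amount

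*Combined protocol and SAP*

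**What the plan says.** All places are in the combined protocol and SAP.

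- **Entry.** The Study population section takes in "biliary AP (with and without concomitant cholecystitis". The Exclusion criteria are only "Patients with AP of etiology other than gallstones; Pregnant patients", so gallbladder inflammation at presentation does not keep a patient out.
- **Baseline recording.** CRF Section 9 (findings on admission) covers bile duct stones, "Cholangitis (Yes/No" and ERCP. Neither it nor any other CRF section records cholecystitis on admission.
- **Outcome recording.** CRF Section 10 (30-day Morbidity) contains "Necrotizing cholecystitis (Yes/No", without date or onset code. Pseudocyst is recorded in the same way.
- **Morbidity outcome.** Under Primary outcomes, a case is a patient "who experienced any type of AP-related complication within 30-days from the hospital admission". New onset is not required, and the meaning of AP-related is not defined.
- **Reason to operate.** Table 1, item 19, lists "Bowel ischaemia or acute necrotizing cholecystitis during acute pancreatitis" among the indications for surgery.
- **Exposure.** CRF Section 12 records cholecystectomy as "Yes-within 3 days/Yes-within 7 days/Yes-within 14 days/No-delayed cholecystectomy", with no indication and no stated day zero. The compliance items under Secondary outcomes include "Use of early definitive treatment strategies, including cholecystectomy and/or ERCP and sphincterotomy".
- **Analysis.** The Statistical analysis section plans logistic models of morbidity and mortality on clinical attitudes and other variables. It gives no covariate list and no rule on the order of exposure and outcome.

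**The concern.** The primary objective asks which guideline items, when disregarded, go with worse outcomes. Early cholecystectomy is one of the items examined. For that item to be read sensibly, the outcome should follow the exposure. Here one component of the outcome may already exist on arrival and may be the reason for the operation. A patient who arrives with necrotizing cholecystitis and is operated on early can enter the data as early surgery followed by morbidity, although the order was the reverse.

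No model can repair this afterwards. There is no baseline field to adjust for, and no date with which to reorder events. If the distinction is not captured during chart abstraction, it cannot be recovered from the dataset.

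A pseudocyst that was already present, for example in a patient with an earlier episode (CRF Section 2 records these), has the same recording gap.

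**Working it through.** The plan gives no figure for this point. Its only design figure, 200 patients per group, concerns mortality in 2019 against 2020 and plays no part here. The documents give no frequency of necrotizing cholecystitis, no morbidity rate and no expected early-cholecystectomy rate for this cohort. **All inputs below are therefore assumptions**, shown as ranges.

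**Set-up, with no true effect of surgery**

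- x = share with necrotizing cholecystitis on admission, all counted as morbid: 1% to 5%
- m = morbidity in everyone else: 15% to 35%
- e1 = probability of early cholecystectomy with the condition: 50% to 80%
- e0 = the same probability without it: 20% to 40%

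The four cells are:

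- a (early, morbid) = x·e1 + (1−x)·m·e0
- b (not early, morbid) = x·(1−e1) + (1−x)·m·(1−e0)
- c (early, not morbid) = (1−x)·(1−m)·e0
- d (not early, not morbid) = (1−x)·(1−m)·(1−e0)

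The odds ratio is ad/(bc).

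**Step 1: necrotizing cholecystitis as the only distortion**

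| x | m | e0 | e1 | a | b | c | d | OR |
|---|---|---|---|---|---|---|---|---|
| 1% | 35% | 40% | 50% | 0.1436 | 0.2129 | 0.2574 | 0.3861 | 1.01 |
| 2% | 25% | 40% | 80% | 0.114 | 0.151 | 0.294 | 0.441 | 1.13 |
| 5% | 15% | 20% | 80% | 0.0685 | 0.124 | 0.1615 | 0.646 | 2.21 |

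The first and last rows are the extremes of the grid. In the middle row, recorded morbidity is 0.114/0.408 = 27.9% with early surgery and 0.151/0.592 = 25.5% without. If e1 = e0 the odds ratio is 1.00, so the upward push requires only that these patients are operated on early more often than the others. If admission cases are moved to baseline and not counted, and their other morbidity runs at the same rate m, the odds ratio returns to 1.00.

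**Step 2: pseudocyst on admission**

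Table 1, item 22, defers cholecystectomy while there are peripancreatic fluid collections. The same formula applies with x now the share with a pseudocyst on admission and e1 below e0. With x = 2%, m = 25%, e0 = 40% and e1 = 10%, the cells are a = 0.002 + 0.098 = 0.100, b = 0.018 + 0.147 = 0.165, c = 0.294 and d = 0.441. The odds ratio is 0.0441/0.0485 = 0.91. The recording gap is the same and the bias is opposite.

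**Step 3: necrotizing cholecystitis together with deferral for other morbidity**

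Now let patients with other morbidity have early cholecystectomy with probability ed = 10% to 30%, with e0 = 40% and e1 = 80%. Applying deferral to all other morbidity is a simplification, since item 22 speaks only of fluid collections. At x = 2%, m = 25% and ed = 20%:

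- item counted: a = 0.016 + 0.049 = 0.065, b = 0.004 + 0.196 = 0.200, c = 0.294, d = 0.441, so OR = 0.0287/0.0588 = 0.49
- item left out: OR = (0.049 × 0.441)/(0.196 × 0.294) = 0.375

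Over the grid (three values each of x, m and ed), the odds ratio is 0.20 to 1.13 with the item counted and 0.17 to 0.64 without it. With the item counted, it exceeds 1 in one of the 27 scenarios.

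**The case against.** A reader might infer that early cholecystectomy will look harmful in this study. The documents do not support that. Step 1 holds other morbidity equal in the two groups, whereas item 22 of Table 1 suggests that patients with fluid collections are operated on later. That concentrates other Section 10 events in the group without early surgery, and step 3 shows the net odds ratio below 1 almost throughout. This objection stands against any claim about net direction. It does not remove the defect: in the central case, counting the item still moves the odds ratio from about 0.38 to 0.49, and two opposing, unmeasured biases do not make an estimate valid.

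A reader might also infer that every admission case is a primary-outcome event on day 0. The plan does not say so. It never states that each positive entry in Section 10 makes a morbidity case, and that section also holds procedures and timing fields. A gallbladder condition that brought the patient in is arguably not AP-related. This stands: such a case can be counted, and the missing definition leaves the decision to each abstractor or analyst.

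The size also depends on how the exposure is defined. If all admission cases are operated early and other morbidity is 15% in both groups, morbidity with early surgery is x/s + (1 − x/s) × 0.15, where s is the share treated early. For x = 1% to 3%, s = 40% gives odds ratios of 1.17 to 1.54. Early definitive treatment under Secondary outcomes also admits ERCP with sphincterotomy. At s = 80%, the definitive-treatment share in the Swedish study cited in the Background, the range is 1.08 to 1.26.

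Finally, the scope is limited to one compliance item and one of the two primary outcomes. That is correct.

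**Conclusion.** The point holds as a recording gap with a known local effect and an unknown net effect. Entry allows cholecystitis, no baseline field records it, and necrotizing cholecystitis can enter the morbidity outcome whether it preceded or followed the operation. Taken alone, this component pushes the early-cholecystectomy association toward harm, with a spurious odds ratio of about 1.0 to 2.2. That range rests wholly on assumed frequencies and on these patients being operated on early more often than others. Pseudocyst on admission pushes the other way, and the documents give nothing from which to settle the balance.

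The 30-day mortality outcome has its own field (CRF Section 13) and is not affected by this miscounting. The 2019 against 2020 morbidity comparison is affected only if the share of admission cases, or the way they are recorded, differs between the years.

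**What to change.** 1. Add to CRF Section 9 a field for cholecystitis on admission that distinguishes necrotizing cholecystitis.
2. Add to CRF Section 10 a present-on-admission tick (Yes/No) for necrotizing cholecystitis and for pseudocyst.
3. In the models relating cholecystectomy timing to morbidity, do not count these two conditions as outcome events when they were present on admission. Enter them as baseline covariates instead, and report a sensitivity analysis in which they are counted.

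The change is confined to those models on purpose. Removing every complication present on admission from the primary outcome would also drop genuine complications of pancreatitis that arose before the patient reached hospital.

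The cost is a few more abstraction fields, which charts should generally be able to fill, and a slightly lower morbidity rate in these models. In the middle scenario of step 1 it falls from 0.02 + 0.98 × 0.25 = 26.5% to 25%, if admission cases have the same rate of other morbidity. If abstraction has closed and charts cannot be reopened, the fallback is a sensitivity analysis that leaves both items out of the outcome, with the limitation stated.
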